5. EXPOSURE TO STUDY MEDICATION

5.1 Exposure Output Specifications

The following data will be presented:

- Number (%) of patients receiving 1, 2, etc. infusions of RTX
- Cumulative dose of RTX by infusion number.
- Total dose, and the number of doses of methylprednisolone prior to first dose of RTX
- Oral corticosteroid treatment duration (months), summarized both descriptively and as number (%) of patients using the following duration categories:
 - Remission induction phase⁽¹⁾
 - <1 month (<26 days)
 - 1 month - <2 months (<45 days)
 - 2 months - <4 months (<105 days)
 - 4 months - <6 months (<165 days)
 - 6 months (≥165 days)
 - Follow-up phase
 - 6 months - <12 months (<335 days)
 - 12 months - <18 months (<515 days)
 - 18 months - <2 years (<699 days)
 - 2 years - <3 years (<1067 days)
 - 3+ years (≥1067 days)
- Total dose of corticosteroid following first dose of RTX.
- duration (months) in the study phases over all patients, summarized as for Methylprednisolone, above

⁽¹⁾ Total duration will be calculated as:

$$1 + \text{Study end date} - \text{Date rituximab first administered}$$

where “study end date” is defined as:

1. For early discontinuation or completion patients: early withdrawal/discontinuation date or date patient completed study

2. For the rest of patients: minimum of common closeout date and last known alive date


ID: EX001SP
 
Rituximab Treatment Exposure by visit during Remission Induction Phase
	
STREAM Template: None
 
Analysis Population: Safety Evaluable Population
 
Analysis Variables: Number of infusions started, Number infusions completed without them being interrupted/modified, Number of patients with interrupted/modified infusions by infusion number, total dose of RTX. The number of infusions categories need to run from 1 (0 for number completed if necessary) to the maximum number of infusions started.
 
Analysis visits to include are: Baseline, Weeks 1 to 3, Months 1, 2, 4, 6
 
Statistics and Calculation Methods: The Infusion Interrupted/Modified rows count the number of Yes's from the "Was the infusion interrupted/modified" question and the denominator for the %s will be the number of patients who started that infusion number and so will correspond to the appropriate row from "Number of infusions started".
 
Percentages are based on:
 
 1. for "Infusion started" section: based on n 2. for "Infusion Interrupted/Modified" section: based on nn*, where nn* is the number of infusions in corresponding visit.
---	---

```

Rituximab
(N=nn)
-----
Infusions started
n                               nn
Baseline                       nn* (xx.x%)
Week 1                         nn* (xx.x%)
Week 2                         nn* (xx.x%)
Week 3                         nn* (xx.x%)
Month 1                        nn* (xx.x%)
...

Infusion Interrupted/Modified
n                               nn
Baseline                       nn/nn* (xx.x%)
Week 1                         nn/nn* (xx.x%)
Week 2                         nn/nn* (xx.x%)
Week 3                         nn/nn* (xx.x%)
Month 1                        nn/nn* (xx.x%)
...

Total number of infusions completed
n                               nn
0                               nn (xx.x%)
1                               nn (xx.x%)
2                               nn (xx.x%)
...

Total cumulative dose (mg)
n                               nn
Mean (SD)                      xxx.x (xx.x)
Median                          xx.x
Q1 - Q3 (IQR)                  xx.x- xx.x (xx.x)
Min - Max                       xx - xxx

```


ID: EX001.1SP
 
Summary of Rituximab Exposure
	
STREAM Template: None
 
Analysis Population: Safety Evaluable Population
 
Analysis Variables: See mock. Percentages are based on n. Include data from Day 1 to common closeout date.
 
- study end date =
 
 1. For early discontinuation or completion patients: minimum of or early withdrawal/discontinuation or patient completed study 2. For the rest of patients: minimum of common closeout date and last known alive date 
Duration of observation = study end date – study start date + 1.
 
Date of last contact is the last available date of efficacy, complete medication start date, laboratory, adverse event assessments, early withdrawal visit, date of last contact or date of death.

---	---

Total number of Infusions administered	
n	nn
Mean (SD)	xxx.x (xx.x)
Median	xx.x
Q1-Q3 (IQR)	xx.x-xx.x (xx.x)
Min - Max	xx - xxx
Total cumulative dose (mg)	
n	nn
Mean (SD)	xxx.x (xx.x)
Median	xx.x
Q1-Q3 (IQR)	xx.x-xx.x (xx.x)
Min - Max	xx - xxx
Duration of Observation (Months)	
n	nn
Mean (SD)	xx.x (xx.x)
Median	xx.x
Q1-Q3 (IQR)	xx.x-xx.x (xx.x)
Min - Max	xx.x - xx.x
Duration of Observation (Months)	
n	nn
Duration ≤ 6	nn (xx.x%)
6 < Duration ≤ 12	nn (xx.x%)
12 < Duration ≤ 18	nn (xx.x%)
18 < Duration ≤ 24	nn (xx.x%)
24 < Duration ≤ 36	nn (xx.x%)
36 < Duration ≤ 48	nn (xx.x%)
48 < Duration ≤ 60	nn (xx.x%)
Duration > 60	nn (xx.x%)
Total patient years of observation	xxx.xx

ID: EX001.2SP

STREAM Template: None

Rituximab
Administration over
Course of study

[figure not shown]
Analysis Population: Safety Evaluable Population

Plot of:

Y-Axis: Patient ID

X-Axis: Study Visit

See mockup.

ID: EX002SP

Listing of Rituximab Administrations, Interruptions and Modifications

STREAM Template: None

Analysis Population: Safety Evaluable Population

Column Variables: Include data from Day 1 to common closout date.

Add "Dose Administered" column in "mg/m²" calculating as follows:

administered dose (mg/m²) = dose administered (mg) / BSA (m²),

where

$$BSA = \text{body surface area} = \text{sqrt} [BW \times Ht / 3600]$$

BW = weight (kg)

Ht = height (cm)

See mockup

Sorting: Sort by center / patient ID and treatment administration day.

Center / Patient ID	Age/Sex/Race	Height (cm) / Weight (kg)	Target Day	Study Day	Study Visit	Planned Dose (mg)	Dose Administered (mg)	Dose Administered (mg/m ²)	Volume Administered (mL)	Infusion Interrupted / Modified	Reason for Modification
ASL.SITEID/AE.PATNUM	ASL.AGE/ASL.SEX/ASL.RACE										
████████	████████	████████	1	1	baseline	xxx	478.8	xxx	xxx	No	
			8	8	week 2	xxx	479.2	xxx	xxx	No	
			15	15	week 2	xxx	479.2	xxx	xxx	Yes	Medication Error
			22	22	month 1	xxx	482.5	xxx	xxx	No	
...											

ID: EX003SP
 
Corticosteroid Treatment Exposure during Remission Induction Phase and Overall
	
STREAM Template: EXT01
 
Analysis Population: Safety Evaluable Population
 
Analysis Variables: Oral steroids: duration of use and total dose.
 
All steroids (all route) total use. This needs discussing with [REDACTED] as she has indicated that she will not be able to supply conversion factors for non-oral steroids.
 
Percentages are based on n.

---	---

Phase: ...

Rituximab
(N=25)

ORAL CORTICOSTEROID DRUGS

Treatment duration (D)

n	25
Mean (SD)	xxx.x (xx.x)
Median	xx.x
Q1 - Q3 (IQR)	xx.x - xx.x (xx.x)
Min - Max	xx - xxx

Treatment duration

n	nn
<1 month (1-25 days)	nn (xx.x%)
1 - <2 months (26-44 days)	nn (xx.x%)
2 - <4 months (45-104 days)	nn (xx.x%)
4 - <6 months (105-164 days)	nn (xx.x%)
6 months (>=165 days)	nn (xx.x%)

Total cumulative oral dose(mg)

n	nn
Mean (SD)	xxx.x (xx.x)
Median	xx.x
Q1 - Q3 (IQR)	xx.x - xx.x (xx.x)
Min - Max	xx - xxx

ALL CORTICOSTEROID DRUGS

Total cumulative dose(mg)

n	nn
Mean (SD)	xxx.x (xx.x)
Median	xx.x
Q1 - Q3 (IQR)	xx.x - xx.x (xx.x)
Min - Max	xx - xxx

ID: EX004SP
 
Listing of Steroid Use
	
STREAM Template: None
 
Analysis Population: Safety Evaluable Population
 
Variables Displayed: See mockup.
 
Sorting: Sort by center / patient ID and treatment administration day.

--	--

Center / Patient ID	Age/Sex/Race ASL.AGE/ ASL.SITEI D/AE.PAT NUM	Height (cm) / Weight (kg) ASL.SEX/ ASL.RACE	Start Day	End Day	Medication	Dose Administered	Unit	Route
██████████	██████████	██████████	1	1	DEXAMETHASONE *	8	mg	Intravenous
			8	9		479.2		
			15	15		479.2		
			22	22		482.5		
██████████	██████████	██████████	1	1		322.5		
			8	8		322.5		
			15	15		322.5		

* GPA/MPA, PRE-RITUXIMAB INFUSION AND GLUCOCORTICOID CONCOMITANT MEDICATIONS

ID: EX006SP

Methylprednisolone
Treatment Exposure
During Screening
Period Prior to **First**
Rituximab Infusion

STREAM Template: EXT01

Analysis Population: Safety Evaluable Population

Analysis Variables: See mockup.

Methylprednisolone (30 mg/kg, up to 1 g/day)
include Methylprednisolone dose on or before Day 1
for the number of doses, include number and percentage of patients
having 1, 2, 3 and >3 doses.

Statistics and Calculation Methods: Percentages are based on n.

[figure not shown]
Sorting: Sort by center / patient ID and treatment administration
day.

	Rituximab (N=nnn)
Treatment duration (D)	
n	nn
Mean (SD)	xx.x (xx.x)
Median	xx.x
Q1-Q3 (IQR)	xx.x-xx.x (xx.x)
Min-max	xx-xx
Number of doses	
n	nn
1 dose	xx.x (xx.x%)
2 doses	xx.x (xx.x%)
3 doses	xx.x (xx.x%)
> 3 doses	xx.x (xx.x%)
Total cumulative dose (mg)	
n	nn
Mean (SD)	xx.x (xx.x)
Median	xx.x
Q1-Q3 (IQR)	xx.x-xx.x (xx.x)
Min-max	xx-xx

ID: EX007SP
 
Patient Profile of Oral Steroid Use
	
STREAM Template: None
 
Analysis Population: Safety Evaluable Population
 
Plot of:
 
Y-Axis: Daily prednisolone equivalent dose (mg)
 
X-Axis: Study Visit
 
One plot for each patient.
 
Reference lines: Draw reference lines through the x-axis on the days of RTX administration.

--	---

Patient Profile of Oral Steroid Use, Safety-Evaluable Patients
Protocol: WA25615

[figure not shown]
Treatment Group: RITUXIMAB (N=25) Center/Patient ID:

ID: EX007.1SP
 
Patient Profiles of Cumulative Glucocorticoid Use
	
STREAM Template: None
 
Analysis Population: Safety Evaluable Population
 
Analysis Variables: Cumulative steroid (Oral and other types in one plot with different shapes/colors) use to Months Weeks 1 to 3 and Months 1, 2, 4, 6, 12 and 18.
 
Plot of:
 
Y-Axis: Cumulative prednisone equivalent dose (mg) to time-points given above.
 
X-Axis: Study Visit
 
One plot for each patient.
 
Reference lines: Draw reference lines through the x-axis on the days of RTX administration.
 
Numeric Precision and Formatting of Statistics: see mockup.

--	--

[figure not shown]
Patient Profiles of Cumulative Oral Glucocorticoid Use, Safety-Evaluable Patients
Protocol: WA25615

Treatment Group: RITUXIMAB (N=25) Center/Patient ID:


ID: EX007.2SP
 
Median Glucocorticoid Use Over Time
	
STREAM Template: None
 
Analysis Population: Safety Evaluable Population
 
Analysis Variables: Median overall steroid use (Oral and other types in two separate plots in one output file) to Weeks 1 to 3 and Months 1, 2, 4, 6, 12 and 18.
 
For IV, include screening period (day -28 to day 1) in the graph.
 
Plot of:
 
Y-Axis: Median overall prednisone equivalent dose (mg) to time-points given above.
 
X-Axis: Study Visit
 
Error Bars: Q1 and Q3.
 
Numeric Precision and Formatting of Statistics: see mockup.

---	---

Laboratory Test: Immunoglobulin Total (g/L)

ID: EX007.3SP
 
Glucocorticoid Use by Visit
	
STREAM Template: None
 
Analysis Population: Safety Evaluable Population
 
Analysis Variables: Glucocorticoid use to Screening, Weeks 1 to 3 and Months 1, 2, 4, 6, 12 and 18.
 
Numeric Precision and Formatting of Statistics: see mockup.

---	--

Visit		Value at Visit
Screening	n	nn
	Median	xx.xx
	Q1 – Q3 (IQR)	xx.xx – xx.xx (xx.xx)
	Min - Max	xx.x – xx.x
Week 1	n	nn
	Median	xx.xx
	Q1 – Q3 (IQR)	xx.xx – xx.xx (xx.xx)
	Min - Max	xx.x – xx.x
...		

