1.2.2 Overall Safety of Rituximab in Rheumatoid Arthritis

Safety data have been collected in clinical trials in a variety of indications, particularly oncology and RA, following IV administration of rituximab.

Safety data are available from 3194 patients with RA who were exposed to rituximab in clinical trials. The total duration of observation is approximately 12,000 patient-years, with 627 patients followed for > 5 years, as of September 2010. The long-term safety profile of rituximab is similar to that observed in the pooled placebo population (the placebo control groups from the randomized RA studies). The rates of infection, myocardial infarction, stroke, and malignancies were consistent with those observed in other RA cohorts. Key findings were as follows (see the Investigator's Brochure for more details):

- Adverse events: The overall rate of AEs (263.1/100 patient-years; 95% CI: 260.21, 266.02), SAEs (14.4/100 patient-years; 95% CI: 13.73, 15.09), and deaths (0.5/100 patient-years; 95% CI: 0.39, 0.65) has remained stable across multiple courses and over time. The most common SAEs were infections (most frequently pneumonia).

- **IRRs:** In total, 23% of all rituximab-treated patients with RA experienced an IRR following the first infusion. Subsequent infusions were better tolerated. Premedication with an IV corticosteroid reduced the proportion of affected patients and severity of events. Most events were mild or moderate and resolved without complication. Less than 1% of patients (16 of the 3194 patients) experienced a total of 18 serious IRRs, none of which was fatal. Of the 18 events, 10 occurred with Course 1 (8 with the first infusion), 5 with Course 2, and 1 each with the first infusions with Courses 4, 5, and 6. The events were variable in nature and included rash, headache, blood pressure changes, anaphylactic or anaphylactoid reactions, and edema. Severe IRRs with fatal outcome have been reported in patients with RA treated with rituximab in the postmarketing setting.

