6.5 PATIENT DISPOSITION AND TREATMENTS

The following data will be listed and summarized for the safety population:

- Patients who completed four IV infusions of rituximab study treatment
- Patients withdrawn prematurely from rituximab study treatment
- Cumulative exposure to rituximab study treatment
- Patients who switched to local standard care
- Details about non-study AAV treatments given over time
- Concomitant medications received
- Patients withdrawn prematurely from study follow-up

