Appendix 7 Procedures for the Intravenous Administration of Rituximab (cont.)

Final Concentration = 1 – 4 mg/mL		
Infusion Rate		Minutes
mg/h ^a	mL/h ^a	
25	(.....)	30
50	(.....)	30
75	(.....)	30
100	(.....)	30
125	(.....)	30
150	(.....)	30
175	(.....)	30
200	(.....)	thereafter

^a For countries not able to set the infusion pump to an accuracy of 0.5 mL/h, the rate is to be rounded down to the nearest whole number.

Subsequent Infusions

Patients who have tolerated the first infusion of rituximab well may receive the second infusion. Infusion schedule described for the first infusion should be used also for all subsequent infusions; the infusion rate can be adjusted if the first infusion was well tolerated. Subject to investigator's discretion, corticosteroid premedication with an IV infusion of 100 mg of methylprednisolone may be administered at least 30 minutes prior to the infusion of rituximab (but not prior to clinical assessments) if the patient has experienced an infusion-related reaction with a previous rituximab infusion.

In the event of the patient experiencing an infusion-related reaction during first or any subsequent infusions, the infusion should be stopped immediately. The patient should be clinically assessed and appropriate treatment should be given as per local policy. The principle investigator or sub-investigator(s) should also be informed as soon as possible and all adverse events should be reported as required in Section 5.2. Once the adverse event has resolved, infusion can be restarted at the previous tolerated rate and should be given at the previous reduced rate for 30 minutes. If tolerated, the rate may be increased to the next closest rate on the patient's infusion schedule. Further information is provided in Section 5.2.3.1.

All rituximab infusions should be made through a dedicated line. After the end of each infusion, the IV line should remain in situ for at least 1 hour in order to be able to administer drugs intravenously if necessary. If there are no adverse events during this period of time, the IV line may be removed.

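### The completed-infusion count in SAP output EX001SP leaves out infusions that were paused or slowed and then given in full, and its row label does not say so

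*SAP*

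**What the plan says.** SAP 5.1 opens with a list of exposure summaries. The first is the number and percentage of patients by how many rituximab infusions they received. EX001SP is the exposure table for the remission induction phase. Its analysis variables begin "Number of infusions started, Number infusions completed without them being interrupted/modified", followed by interrupted or modified infusions by infusion number, and total dose. An instruction on categories follows: "The number of infusions categories need to run from 1 (0 for number completed if necessary) to the maximum number of infusions started". Interruption and modification are captured together by a single yes/no question. In the mock-up, the corresponding row is "Total number of infusions completed", with categories 0, 1, 2 and so on. Neither the label nor a footnote carries the condition about interruption.

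Protocol 6.5 lists, among the items to be summarized, "Patients who completed four IV infusions of rituximab study treatment". Protocol Appendix 7 says that at an infusion-related reaction (IRR) "the infusion should be stopped immediately", and it allows a restart once the event has resolved. Protocol 5.2.3.1 likewise expects that the infusion can be resumed in most cases, at a reduced rate.

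**The concern.** The variable text and the row label describe two different quantities. The text counts infusions that ran without a pause or rate change. The label tells the reader how many infusions were completed. A child whose infusion is stopped for a reaction, restarted and given in full has completed it in the ordinary sense and in the sense of Protocol 6.5, but not in the sense of the EX001SP text.

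The row is the natural source for the per-patient item in SAP 5.1 and for the four-infusion item in Protocol 6.5. With 25 children, each one placed in a lower category moves a reported percentage by 1/25 = 4 percentage points. A reader of the finished table sees only the label, and would take a managed reaction for an infusion that was not finished. Two programmers could also produce different tables from the same specification, one following the text and the other the mock-up.

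**Working it through.** **1. The definitions side by side**

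| Place | Quantity | Condition on interruption |
|---|---|---|
| EX001SP, variable text | "Number infusions completed without them being interrupted/modified" | Yes |
| EX001SP, mock-up row | "Total number of infusions completed" | None stated |
| SAP 5.1, opening list | Patients by number of infusions received | None |
| Protocol 6.5 | Patients completing four infusions | None |

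The category instruction fits the variable text. It allows a zero for the completed count only, although everyone in the safety population started at least one infusion.

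**2. The rule applied**

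Take a child who starts four infusions and receives the full dose each time, with k of them paused or slowed. By the EX001SP text the count is 4 − k; by dose delivered it is 4.

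| k | EX001SP text | Full dose delivered |
|---|---|---|
| 0 | 4 | 4 |
| 1 | 3 | 4 |
| 2 | 2 | 4 |
| 3 | 1 | 4 |
| 4 | 0 | 4 |

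Protocol 5.2.3.1 and Appendix 7 describe the resumed rate differently and should be reconciled. That does not affect this count, because under either description the stop itself makes the answer to the interrupted/modified question a yes.

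**3. Whether another output gives the count**

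- In the EX001SP mock-up, infusions started and infusions interrupted or modified are shown by visit, not per patient.
- EX001.1SP gives the number of infusions administered as mean, median, quartiles and range, from Day 1 to common closeout, so retreatment after Month 6 is mixed in.
- DS002SP has a row for completion of planned rituximab treatment, with no visible definition and no count of infusions.
- EX002SP lists planned dose, administered dose and the interruption flag for each infusion. The correct count can be rebuilt from it, patient by patient.

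**4. Size, as illustration only**

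The plan states no figure that depends on this definition, so there is none to reproduce. Let p be the probability that a child's first infusion is interrupted or modified. Assume no interruption later, every interrupted infusion finished, and 25 children (the planned sample size).

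Expected number shown below four = 25 × p. Chance of at least one such child = 1 − (1 − p)^25.

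- p = 5% (assumed): 25 × 0.05 = 1.25 children; 1 − 0.95^25 = 0.72.
- p = 10% (assumed): 25 × 0.10 = 2.5 children; 1 − 0.90^25 = 0.93.
- p = 23%: 25 × 0.23 = 5.75 children; 1 − 0.77^25 = 0.998.

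The 23% is borrowed from adults with rheumatoid arthritis (Protocol 1.2.2): "In total, 23% of all rituximab-treated patients with RA experienced an IRR following the first infusion". It is an IRR rate, not an interruption rate.

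Interruptions at later infusions would raise these figures. With 5% at each of the four infusions, assumed independent, the share is 1 − 0.95^4 = 0.185, or 4.6 of 25. Interrupted infusions that are never finished would lower them.

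One edge case: the EX001SP visits run to Month 6, whose analysis window ends at Day 210. A retreatment infusion in that window could bring a child's count back to four.

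**The case against.** The strongest reply is that the variable states its own condition and looks deliberate: the text spells it out and the zero category anticipates it. The number of uninterrupted infusions is a legitimate tolerability summary. The same table shows started and interrupted infusions by visit and the cumulative dose, and EX002SP holds the detail. Restoring the qualifier in the label would remove the misreading. Completion of infusions is not a listed outcome measure, and the study tests no hypothesis.

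Much of this stands. The fault is confined to one row, no primary safety or PK measure uses it, and exposure can be recovered. What does not stand is that other outputs already supply the count. As step 3 shows, none of the readable mock-ups gives it per patient for the induction phase, so relabelling alone would leave the SAP 5.1 and Protocol 6.5 items without a defined source.

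The reply is also right to resist a large estimate. SAP section 6 counts reactions during an infusion or in the 24 hours after it, and a reaction after the end interrupts nothing. These children receive IV methylprednisolone before the first infusion, although possibly days earlier, and Protocol 1.2.2 reports that IV corticosteroid premedication reduced the proportion of patients affected. Protocol 5.2.3.1 requires permanent discontinuation for some reactions, and those infusions are rightly not completed. In the other direction, the flag also covers interruptions for reasons other than reactions.

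**Conclusion.** The point holds as a definition and labelling fault in one row of EX001SP. As written, the row omits infusions that were paused or slowed and then fully given. It therefore differs from the quantities named in Protocol 6.5 and SAP 5.1, and its label hides the difference. It is worth correcting because this is the only per-patient infusion count for the induction phase in the readable outputs, and because text and label have to be reconciled in any case.

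The size is not known. Under the assumptions in step 4, with no later interruptions, it is about 1.3 children of 25 at a 5% first-infusion interruption rate and about 5.8 at 23%. The upper figure uses a borrowed adult reaction rate and gives scale, not a forecast.

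Three stronger readings go beyond the documents. A reader might infer that a quarter or more of the children would be misreported; that would need the adult IRR rate to be an interruption rate and every such infusion to be finished, and neither is established. A reader might infer that the row would contradict the table's cumulative dose or DS002SP. Dose and uninterrupted infusions are different quantities, and the DS002SP row has no visible definition, so disagreement there is possible but not shown. Finally, a reader might infer that exposure information is lost, which EX002SP rules out.

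**What to change.** In EX001SP:

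- Define an infusion as completed when the planned dose was administered within a stated tolerance, whether or not it was paused or slowed. The tolerance is needed because exact equality of planned and administered milligrams could create false incompletes.
- Report the number and percentage of children with four completed infusions, so that the table answers Protocol 6.5.
- Keep the present per-patient count as a separate row, with the no-interruption-or-modification condition in its label. It remains useful as a tolerability measure.

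The cost is a few lines of SAP and mock-up text, one extra row and a tolerance to agree. No new data are needed, because planned and administered dose are already columns in EX002SP.

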4.3.2 Dosage, Administration, and Compliance

4.3.2.1 Rituximab (Investigational Medicinal Product)

4.3.2.1.1 Dosage and Administration

For this trial, rituximab will be given as an IV infusion of 375 mg/m² once a week for 4 consecutive weeks, starting at the baseline visit. The dose for rituximab will be calculated according to the participant's BSA at the screening visit after the participant's eligibility has been established, and it will remain the same for all four infusions. Each participant's actual body height and weight, measured during the 28-day period before baseline (i.e., during the 28 days before the start of administration of open-label rituximab) will be used to calculate a patient's BSA according to the Dubois formula ([DuBois and Dubois 1916](#)):

$$\text{BSA (m}^2\text{)} = [(\text{Weight in kg})^{0.425} \times (\text{Height in cm})^{0.725}] \times 0.00718$$

Note: Do not round until the end of the calculation.

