4.3.4 Retreatment with Rituximab

After Month 6, if patients require retreatment with rituximab, further courses will be provided by the Sponsor until the common closeout date. The dose of rituximab and the frequency of retreatment for the maintenance of remission will be at the discretion of the investigator.

Following administration of the first infusion the investigator should review the following safety criteria before administering subsequent infusions of rituximab.

The following are absolute contraindications to receipt of further infusions of rituximab in this study:

- An infusion reaction which necessitated complete discontinuation of the study infusions
- Significant deterioration in patient's general health status since inclusion into the study that results in the patient meeting the exclusion criteria related to General Health
- Emergent primary or secondary immunodeficiency recognized during the study period, including new HIV infection, de novo hepatitis B, hepatitis C, or active tuberculosis infection

Patients who have any of the absolute contraindications to receipt of study infusions with rituximab will be withdrawn from the study and should be encouraged to enter Follow Up.

Patients who develop malignancy during the study will not be able to receive further courses of treatment with the study medication. However, patients with basal cell carcinoma, squamous cell carcinoma of the skin or melanoma in situ (Clarke's Level I), or cervical carcinoma in situ with no stromal invasion (stage 0), which have been completely excised and can be considered as cured, may be retreated with study medication at the discretion of the investigator.

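### Two minor definition errors in the SAP 5.1 exposure outputs: the mg/m² column of EX002SP uses a different BSA formula from the one that sets the induction dose, and footnote (1), as printed, makes oral-steroid duration equal to time on study

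*SAP*

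**What the plan says.** **Rituximab dose per m².** Protocol 4.3.2.1.1 derives the induction dose from the "BSA according to the Dubois formula", using height and weight measured in the 28 days before baseline. It adds that "it will remain the same for all four infusions". The printed formula is weight^0.425 × height^0.725 × 0.00718.

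In SAP 5.1, EX002SP adds a column defined as "dose administered (mg) / BSA", where BSA is √(weight × height/3600). Its scope is "Include data from Day 1 to common closout date", so retreatment infusions are included. For these, protocol 4.3.4 says: "The dose of rituximab and the frequency of retreatment for the maintenance of remission will be at the discretion of the investigator".

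**Oral-steroid duration.** SAP 5.1 lists oral corticosteroid duration, with categories for each phase. Marker (1) stands on the remission induction heading of that item. The footnote begins "Total duration will be calculated as" and gives 1 + study end date − date of first rituximab. Study end is the withdrawal or completion date or, for other patients, the "minimum of common closeout date and last known alive date". EX003SP, which tabulates the same item, describes it as how long oral steroids were used. The last bullet of the list, "duration (months) in the study phases over all patients", carries no marker.

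**The concern.** The mg/m² column puts each infusion on the protocol's own 375 mg/m² scale, so a reader will compare it with 375. If the divisor is not the BSA that produced the dose, a correctly dosed child shows a departure that comes from the formula and not from the dosing. In a listing of administrations, interruptions and modifications, that invites needless queries.

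The footnote contains no steroid date. Attached to steroid duration, it would report how long the child was followed, and the shorter categories would count early study departures, not early steroid stopping. It also has no cap at Month 6, although SAP 1 ends the induction phase there.

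**Working it through.** **Part 1: listed mg/m² for a child dosed exactly to protocol**

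Inputs: 375 mg/m² and the DuBois formula (protocol 4.3.2.1.1); √(w × h/3600) (SAP EX002SP). The documents give no body-size distribution, so the sizes below are assumptions.

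Listed value = 375 × [w^0.425 × h^0.725 × 0.00718] / √(w × h/3600).

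Since √3600 = 60 and 0.00718 × 60 = 0.4308, this reduces to 375 × 0.4308 × (h³/w)^0.075. The error depends only on h³/w. It is zero at 75,218 cm³/kg, −1% at about 65,800 and +1% at about 85,900.

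| Assumed size (kg/cm) | DuBois BSA | EX002SP BSA | Listed mg/m² | Difference |
|---|---|---|---|---|
| 10/80 (toddler) | 0.4580 | 0.4714 | 364.3 | −2.8% |
| 12/87 (toddler) | 0.5259 | 0.5385 | 366.2 | −2.3% |
| 16/102 | 0.6670 | 0.6733 | 371.5 | −0.9% |
| 20/115 | 0.8000 | 0.7993 | 375.3 | +0.1% |
| 32/138 | 1.1149 | 1.1075 | 377.5 | +0.7% |
| 40/150 | 1.3022 | 1.2910 | 378.2 | +0.9% |
| 50/162 | 1.5139 | 1.5000 | 378.5 | +0.9% |
| 65/175 | 1.7898 | 1.7776 | 377.6 | +0.7% |
| 45/170 (thin) | 1.4990 | 1.4577 | 385.6 | +2.8% |
| 80/160 (heavy) | 1.8320 | 1.8856 | 364.3 | −2.8% |
| 100/160 (heavy) | 2.0142 | 2.1082 | 358.3 | −4.5% |

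With DuBois and the screening measurements in the listing, every row would read 375.0.

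**Part 2: footnote (1) taken literally**

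Inputs: visit windows from protocol Appendix 2 (Month 6 = Day 180 ± 5; Month 18 = Day 545 ± 10) and the top induction category in SAP 5.1 (165 days or more). First rituximab is Day 1, so duration = 1 + end day − 1 = end day.

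- Earliest in-window Month 6 visit: 180 − 5 = Day 175. A patient whose study ends there gets 175 days, already in the top category.
- Earliest in-window Month 18 visit: 545 − 10 = Day 535. A patient who reaches it gets at least 535 days for a phase planned to end at Day 180.
- Illustration: 90 days of oral steroid, followed to Day 545. By use, the patient belongs in the 2 to <4 month category (45–104 days). By the footnote the value is 545 days, in the top category.

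**Where the footnote fits.** Its end-date rule is the one EX001.1SP uses for duration of observation, and it refers to total duration. Both suggest that it was written for time on study.

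**The case against.** **On the listing.** EX002SP prints planned mg beside administered mg, and that pair shows without any BSA formula whether the intended dose was given. Height and weight are on the same listing, so a reader can recompute. Mid-range differences are below 1%, and the larger figures rest on assumed sizes. All of this stands and is why the point is minor. It does not make the column right.

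**On retreatment.** A reader might infer that the SAP leaves the height and weight for these infusions wholly open. That goes too far. The mockup shows one height and weight entry per patient, SAP 3.2.1 defines baseline as the last pre-treatment value, and 3.2.2 carries it into follow-up. The natural reading is a single patient-level value, although EX002SP does not say so. The lack of a protocol mg/m² target for retreatment is no defect in a descriptive column.

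**On the footnote.** This is probably a misplaced marker. The EX003SP wording points to actual use, EX004SP lists steroid start and end days, and template EXT01, cited by EX003SP, is not in the documents. A reader might infer that no other rule exists, or that the steroid table is bound to be wrong; neither can be shown. A reader might also infer that most patients would be misclassified. Protocol 4.3.2.3.1 tapers oral steroid to a minimum by Month 6 and does not require stopping, so many patients belong in the top category anyway. What remains is that the printed text conflicts with EX003SP, and a programmer may follow it.

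**Conclusion.** Both definitions are wrong as written, and both are minor.

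The EX002SP conflict is certain, because two different formulas are stated. Its size depends on the assumed body sizes: within 1% when h³/w lies between about 65,800 and 85,900 cm³/kg, and −4.5% to +2.8% over the sizes tried. It affects one listing column. It does not suggest that any child would be misdosed.

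The footnote conflicts with EX003SP as printed, most likely through a misplaced marker. If it were followed, the category error would fall on patients who stop or interrupt oral steroid early, and the descriptive days would exceed the induction phase for patients who stay on study.

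The rituximab mg summaries (EX001SP, EX001.1SP) and the primary safety and PK outcomes are untouched.

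**What to change.** **EX002SP.** For the four induction infusions, compute mg/m² with the protocol's DuBois formula and the screening height and weight that set the dose. For retreatment infusions, confirm in the specification whether the single patient-level height and weight implied by the mockup and SAP 3.2.1–3.2.2 is used.

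**Footnote (1).** Remove the marker from oral-steroid duration. Derive that duration from the steroid start and end days listed in EX004SP, truncated to the start and end of each phase. The printed follow-up categories begin at 6 months, so also say whether follow-up days count from Day 1 or from the start of the phase. Keep the footnote formula only for total duration of observation, consistent with EX001.1SP. Moving the marker to the last bullet would not be enough: duration in the study phases is also per phase, and an uncapped total does not give it. Apply the phase start and end dates of the SAP there.

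**Cost.** SAP wording and minor programming. Height, weight and steroid start and end days are already collected.
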